1 CUHK Achilles Tendon Disorder Registry

2 **Research Project Statement**

3 The Achilles tendon is one of our body's most important structures, and the 'Achilles heel' is
4 a real clinical problem. The management of its pathologies—spanning acute ruptures to
5 chronic tendinopathies—remains heterogeneous, with a critical absence of high-quality
6 longitudinal data to compare treatments and guide personalized rehabilitation strategies. To
7 address this evidence gap, we will establish a comprehensive prospective Achilles Tendon
8 Disorder Registry.

9 The registry will integrate our team's expertise in Achilles tendon research, which
10 encompasses standardized assessment tools, biomechanical studies, and treatment evaluation.
11 By systematically collecting outcome data, it will enable us to: determine the effectiveness of
12 different treatment methods, advance evidence-based knowledge, improve the quality of care,
13 enhance patient safety, achieve better patient outcomes, and reduce healthcare costs. This
14 longitudinal registry will monitor long term outcome of Achilles tendon problem, and track
15 Achilles tendon treatment outcomes, thereby helping to inform precision rehabilitation
16 strategies and reduce long-term disability in the future.

17 **Research Questions**

- 19 1. Does the baseline status (e.g., vascularity and elastography metrics) influence the
20 prognosis?
- 21 2. Does pre-existing Achilles tendinopathy increase the risk of acute Achilles tendon rupture?
- 22 3. Which group of patients is more responsive to which treatment?

23 **Hypothesis**

- 25 1. Baseline status (e.g., vascularity and elastography metrics) significantly influences
26 prognosis.
- 27 2. Pre-existing Achilles tendinopathy significantly increases the risk of acute Achilles tendon
28 rupture.
- 29 3. Different patient groups respond differently to various treatment methods.

31 **Research Methodology**

32 **Study setting**

33 This prospective cohort study will be conducted at the Prince of Wales Hospital in Hong
34 Kong. All self-reported, functional, and ultrasonographic outcomes will be assessed at
35 baseline, 6 weeks, 3 months, 6 months, and 1 year. Following the initial 1-year follow-up, all
36 self-reported outcomes will be assessed annually through online questionnaires at 2, 3, 4, and
37 5 years. All participants must provide written informed consent prior to enrolment. The

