38 investigator will obtain and document consent before any study procedures are performed.
39 All eligible participants will be fully informed about the study and given ample time to
40 consider participation; the research team will answer all participant questions. The trial will
41 be conducted in accordance with the Declaration of Helsinki.

42 **Eligibility**

43 Inclusion:

- 45 • Adults (>18 years of age)

47

48 Exclusion:

49

50

51

52

53

54

- 55 Any physical or psychological comorbidity that would impair the ability to complete study assessments (e.g., significant neurological deficits) or preclude the provision of informed consent.
- Concomitant diseases that severely affect lower limb function or assessment (e.g., severe osteoarthritis of the knee or hip, prior lower limb amputation, peripheral vascular disease, active rheumatoid arthritis, lower limb paralysis, etc.)

56 **Outcome measures**

57 Baseline demographic data will be collected, including age (date of birth), gender (biological sex), occupation, recreational activity (Pre-injury and current activity levels -Tegner score), diagnosis (types of Achilles tendon problem) , treatment modalities already tried.

60 Time frames for collection include 0 weeks (baseline), 6 weeks, 3 months, 6 months, 1 year. Following the initial 1-year follow-up, all self-reported outcomes will be assessed annually through online questionnaires at 2, 3, 4, and 5 years.

64 **Primary Outcome: Victorian Institute of Sports Assessment (VISA-A) Questionnaire**

65 The primary outcome measure will be the Victorian Institute of Sport Assessment (VISA-A) questionnaire, available in either the original English or validated Chinese version, depending on the participant's native language. This specific scoring system developed for the Achilles tendon is the most widely used score for clinical Achilles research. The VISA-A is scored on a scale of 0 to 100; lower scores indicate more severity of symptoms, while a score of 100 indicates a healthy and pain-free Achilles tendon.

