133 tendons will be imaged bilaterally using an ultrasound machine equipped with a 12 MHz
134 linear transducer (Aixplorer, SuperSonic Imagine, Aix-En-Provence, France). All regions of
135 interest (ROIs) will be measured at: (1) the maximum thickness point, and (2) standardized
136 locations 2 cm, 4 cm, and 6 cm proximal to the insertion.

137 **Tendon thickness:** Using B-mode ultrasound scanning, the probe is moved from the medial
138 to the lateral aspect of the Achilles tendon until a planar image of the Achilles tendon is
139 clearly shown. The probe was adjusted straight perpendicular to the tendon fibres. A
140 greyscale sonogram is acquired, and the tendon thickness is measured at the maximum
141 thickness point and at 2, 4, 6 cm proximal to the insertion. Less than 5.3 mm was considered
142 a healthy value for the Achilles tendon.

143 **Tendon vascularity:** Vascularity will be documented using the Ohberg score. Using the
144 Doppler mode on the ultrasound machine, the transducer is placed vertically to obtain a
145 sagittal view of the softest area of the Achilles tendon. Pressure on the skin from the

146 transducer should be kept to a minimum to prevent occlusion of blood vessels. The colour
147 box is focused on the dorsal aspect of the tendon. The assessor will spend one minute
148 exploring the blood flow over the tendon to find the area of maximum Doppler flow. After
149 locating the area, sonograms are taken to determine the Öhberg score. The Öhberg score
150 ranges from 0 to 3 points. In this scoring system, the score is defined as 0 (no
151 neovascularisation, healthy), 1 (mild neovascularisation with a few single vessels), 2
152 (moderate neovascularisation with a moderate number of mostly transverse vessels), and 3
153 (multiple, mostly transverse vessels distributed throughout the depth of the tendon). Higher
154 scores indicate more Doppler blood flow in the peritendinous and intratendinous tissues.
155 Healthy tendons (Ohberg score of 0) have no blood vessels in the Achilles tendon.

156 **Tendon elasticity :**

157 Shear wave elastography (SWE) can be used to quantify soft tissue stiffness. Once the
158 optimal scan plane of the tendon is determined, the SWE function is activated. It enters
159 penetration mode and the measured stiffness range is normalized to 0-600 kPa. The SWE
160 color card (H × W: 1.4 cm × 1.3 cm) is placed immediately above the upper edge of the

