161 calcaneus. After the color signal stabilized for five seconds, the elastogram was recorded and
162 stored. Tendon stiffness was measured using a Q-box stiffness meter. Depending on the size
163 of the tendon, the diameter of the circular measuring area (Q-box) is set to 2 mm, which
164 covers the Achilles tendon and excludes other adjacent soft tissues. The Q-box is located in
165 the center of the maximum thickness point and 2, 4, 6 cm proximal to the calcaneal insertion
166 site. For each Q-box, the average tendon stiffness (in kPa) is measured.

167 **Tendon oxygenation and vascularity:** The pathological tendon's oxygenation and
168 vascularity were quantified using a multiwavelength photoacoustic ultrasound (PAUS)
169 system equipped with a 7Hz probe and dual-wavelength LED sources (850nm/750nm). The
170 participant assumes a prone position with heels extended beyond the examination table. The
171 probe is positioned on the target tendon, with mode-specific presets selected ("Deep PA" for
172 vascularity at 850nm; "Deep Oxy" for oxygenation at 750nm). Each 20-second acquisition
173 captures 200 frames, with two repeated scans per mode to ensure data reliability.

174 **Thermographic tendon temperature:** Participants will be advised to avoid physical
175 exercise and hot baths before the procedure to ensure data reliability. Each participant will
176 rest in a seated position for 10 minutes followed by 2 minutes without socks. The room will
177 be maintained at 20-24°C. The infrared camera will be positioned one meter from the
178 participant, using a ThermaCam FLIR-T8210. Images will be analyzed with ThermaCAM
179 Researcher Pro 2.8 SR-1 software, and a rectangular area covering the Achilles tendon will
180 be used for temperature assessment.

181

182 **Sample size**

183 As a prospective registry study, this study plans to consecutively enroll all eligible patients
184 presenting to the Prince of Wales Hospital between 2025 and 2028. Based on the annual
185 patient volume, a minimum of 500 participants is expected to be recruited, which is
186 anticipated to provide sufficient statistical power for the planned multivariable analyses.

187

188 **Recruitment**

189 Participants will be recruited through multiple concurrent strategies. Our primary recruitment
190 site is the Prince of Wales Hospital. We will also utilize our sports medicine network, which

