191 includes school sports teams, professional organizations (e.g., Kitchee Football Club), and an
192 extensive alumni network of doctors and sports medicine professionals from our MSc
193 program. Simultaneously, study advertisements will be distributed to all staff and students of
194 The Chinese University of Hong Kong through the CUHK Mass Mail System to ensure
195 comprehensive outreach.

196

197 **Data collection and management**198 **Plans to promote participant retention and complete follow-up:** The schedule for all the
199 outcome measure appointments will be provided from the beginning. For patients who have
200 missed their scheduled appointments for follow-up assessments, additional hours will be
201 extended to the evenings at the Sports Performance and Biomechanics laboratory at CUHK
202 so that participants may come for assessment (e.g., after work, rescheduled due to illness,
203 etc.).204 **Data management:** Data collected will be securely stored in password-protected computers
205 and archived for five years after publication. The Principal Investigator (PI) and research
206 assistants will oversee data collection, entry, and analysis. To ensure accuracy, a double data
207 entry method and range checks will be implemented. Data will be restored into an Excel files
208 and then transferred to SPSS software for analysis.209 **Confidentiality:** To ensure the highest level of privacy and security, the Sports Performance
210 and Biomechanics Laboratory stores all personal information and consent forms in securely
211 locked cabinets. Our online electronic database is protected by password-protected computers,
212 ensuring the utmost confidentiality. Access to the collected data is strictly limited to trusted
213 trial team members, with no access granted to participants. De-identified participant data may
214 be shared with other researchers upon reasonable request and after execution of appropriate
215 data sharing agreements, subject to approval by the ethics committee.

216 There is no plan for using biological specimens outside of this study plan.

217 **Statistical methods for primary and secondary outcomes:** Statistical analyses will be
218 performed using SPSS (version 28.0), with a two-sided significance level of $\alpha = 0.05$.
219 Continuous outcomes (e.g., VISA-A, NPRS, tendon thickness, dynamometry) will be
220 summarized as mean \pm standard deviation, assessed by Shapiro–Wilk test. Categorical

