221 variables will be presented as frequencies and percentages.222 To address Q1 (prognostic influence of baseline status), multivariable linear or logistic
223 regression models will be constructed to evaluate the association between baseline metrics
224 (e.g., vascularity, elastography) and functional outcomes (e.g., VISA-A, heel raise capacity),
225 adjusting for covariates such as age, sex, and symptom duration.226 For Q2 (risk assessment), a Cox proportional hazards model or logistic regression will be
227 used to examine whether pre-existing tendinopathy (dichotomized: yes/no) predicts
228 subsequent acute rupture, with results reported as hazard ratios or odds ratios and 95%
229 confidence intervals.230 For Q3 (treatment responsiveness), interaction terms between patient subgroups (e.g., defined
231 by baseline severity, structural metrics) and treatment types will be incorporated into
232 regression models to identify effect modifiers. Should significant interactions be detected,
233 stratified analyses will be performed.234 **Interim analyses:** An interim analysis will be performed on the primary endpoint when 20%
235 of participants completed the 1-year follow-up. The interim analysis ensures that no serious
236 adverse event happened during the study period.237 **Methods in analysis to handle protocol non-adherence and any statistical methods to
238 handle missing data:** Missing data will be handled using multiple imputation under the
239 missing-at-random assumption. Sensitivity analyses will include complete-case assessments.
240 Model assumptions (e.g., linearity, proportionality) will be verified graphically and
241 analytically.242 **Plans to give access to the full protocol, participant-level data, and statistical code:** The
243 protocol will be registered on clinicaltrials.gov. The participant-level data and statistical code
244 can be provided upon request.

245 **Oversight and monitoring:** The principal investigator will monitor the progress of the study.
246 The trial steering committee consists of research team members who will participate in
247 participant recruitment, data collection, and management. The trial steering committee
248 consists of orthopaedic surgeons and researchers (research assistants and biostatisticians).
249 The orthopaedic surgeons and research assistants will participate in data collection and
250 analysis. The biostatistician will monitor data collection and perform interim analysis. There

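### Q3 tests effect modification through subgroups of mostly continuous baseline measures; under a normal, linear model a two-way split loses at least about 36% of the information, and three to five equal groups about 10–21%

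*Protocol*

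**What the plan says.** The third item under Research Questions in the protocol asks: "Which group of patients is more responsive to which treatment". The matching paragraph in the section on statistical methods for primary and secondary outcomes begins "For Q3 (treatment responsiveness), interaction terms between patient subgroups (e.g., defined" and continues "by baseline severity, structural metrics) and treatment types will be incorporated into" "regression models to identify effect modifiers. Should significant interactions be detected". If an interaction is significant, stratified analyses follow.

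The number of subgroups and the cut-points are not given. Thickness has one threshold, 5.3 mm, but it is described as the limit of a healthy value and is not tied to Q3. A two-way split is stated only for Q2, where pre-existing tendinopathy is coded yes or no.

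On measurement scales the protocol is clear:
- VISA-A: "The VISA-A is scored on a scale of 0 to 100", with lower scores meaning more severe symptoms.
- VISA-A and tendon thickness are both listed as continuous: "Continuous outcomes (e.g., VISA-A, NPRS, tendon thickness, dynamometry) will be" summarised by mean and standard deviation.
- Elastography: for each measuring area, "the average tendon stiffness (in kPa) is measured".
- Neovascularity is the exception. The Öhberg score "ranges from 0 to 3 points" and is already ordinal.

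**The concern.** Q3 asks how the difference between treatments changes with a patient's baseline state. When that state is measured on a continuous scale, forming groups first treats everyone within a group as identical and makes the result depend on where the boundaries fall. The stratified follow-up carries that dependence into the reported estimates.

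Interactions are estimated less precisely than main effects, and Q3 is one of only three research questions. The planned minimum of 500 participants comes from expected patient volume. The Sample size section anticipates sufficient power for the multivariable analyses but shows no effect size or power calculation. The analysis therefore has no demonstrated margin from which to give up information.

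**Working it through.** **The plan's own figure.** The protocol gives 500 participants as a volume-based minimum, with no effect size, standard deviation or power. There is nothing to reproduce, so the check asks what grouping costs relative to keeping the modifier continuous.

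**Inputs**
- From the protocol: minimum n = 500; two-sided α = 0.05.
- Assumed: the modifier is roughly normal; the treatment difference changes linearly with it; the continuous interaction would have 80% power (a reference point only).

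**Step 1: information retained.** The fraction kept is the squared correlation between the modifier and its grouped version. With groups bounded by a and b, and p the proportion in each group:

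retained = Σ (φ(a) − φ(b))² / p

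For a single cut at c with proportion q below it, this reduces to φ(c)² / (q(1 − q)). At the median, 0.3989² / 0.25 = 2/π = 0.637.

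| Grouping (normal modifier) | Retained | Lost | 500 act like |
|---|---|---|---|
| Two groups, 50/50 | 0.637 | 36.3% | 318 |
| Two groups, 70/30 | 0.576 | 42.4% | 288 |
| Two groups, 80/20 | 0.490 | 51.0% | 245 |
| Three equal groups | 0.793 | 20.7% | 397 |
| Four equal groups | 0.861 | 13.9% | 430 |
| Five equal groups | 0.897 | 10.3% | 449 |

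The last column is 500 × retained. The median is the best place for a single cut of a normal modifier, so 36% is the least a two-way split can lose under these assumptions. Optimal rather than equal cuts reduce the loss to 19.0%, 11.8% and 8.0% for three, four and five groups.

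**Step 2: sensitivity to the distribution.** For a uniform modifier cut into k equal groups the loss is 1/k²: 25% for two groups, 11.1% for three and 6.2% for four.

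**Step 3: effect on power.** If the continuous interaction has 80% power, its expected z is 1.960 + 0.842 = 2.802. After a median split, power = Φ(2.802 × √0.637 − 1.960) = Φ(0.276) ≈ 0.61. With more groups the result depends on the test:

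| Equal groups | Unordered groups, k − 1 df | 1-df trend across groups |
|---|---|---|
| 2 | 61% | 61% |
| 3 | 60% | 70% |
| 4 | 57% | 74% |
| 5 | 54% | 76% |

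The low figures in the middle column come partly from the extra degrees of freedom, not only from information lost by grouping.

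**Step 4: simulation check.** With n = 500, two treatments assigned with equal probability, a normal modifier and an interaction of 0.25 residual SD per SD of modifier (3,000 replicates for each analysis), power was 78% with the continuous term, 58% with a median split and 69% with a tertile score. This agrees with the formulas.

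**The case against.** The strongest reply is that the protocol never commits to a two-way split. Group numbers and cut-points are commonly left to the SAP, which is not shown, and the variables are introduced only as examples. Some candidate modifiers, such as diagnosis type and Öhberg grade, are truly categorical or ordinal. The protocol's Q1 paragraph uses baseline metrics in regression with no mention of grouping, and linearity is to be checked, so there is no sign of a general policy of categorising.

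Much of this stands, and it limits the point. A reader might infer that Q3 necessarily discards a third or more of the information. The document does not support that, because the figure needs two groups and a roughly normal modifier. A reader might also infer that cut-points will be picked after seeing the data, or that severity will be left uncontrolled within bands. The Q3 text says neither: it gives no cut-points, and it does not exclude continuous severity from the models. The research question itself is plain language and would read the same under a continuous analysis.

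The reply does not remove the core. The examples qualify which variables define the subgroups, not whether subgroups are used. An SAP that supplied cut-points would be filling in a grouping that the protocol has already adopted.

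Two further cautions are fair. The 80% starting power is a reference point, not a protocol figure. And if modification is threshold-like rather than linear, the calculation does not apply as it stands.

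**Conclusion.** The point holds in conditional form. The protocol specifies subgroup-by-treatment interactions for baseline measures that are mostly collected on continuous scales, and a better analysis of the same data is available. With a roughly normal modifier and linear modification, a two-way split loses at least about 36% of the information, taking 80% power to about 61%; three to five equal groups lose about 10–21%. For a uniform modifier, a median split loses 25%.

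Which of these applies cannot be known from the protocol. The absence of group numbers and cut-points is not itself the criticism. This is a change the sponsor should make; it does not invalidate the registry.

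**What to change.** Reword the Q3 paragraph along these lines: *Continuous modifiers (such as baseline VISA-A, tendon thickness and stiffness) will enter as continuous terms multiplied by treatment type. The term will be linear by default, with a restricted cubic spline of low degrees of freedom where non-linearity is evident and numbers per treatment allow. The estimated treatment difference will be shown with a 95% confidence band across the modifier range. Subgroups will be used for categorical or ordinal modifiers (such as sex, diagnosis type and Öhberg grade) and for display.*

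This needs no new data, visits or participants. The cost is in the modelling. A spline adds degrees of freedom for every treatment contrast: with four treatment types (an assumption), there are three contrasts, so a four-knot spline with three terms uses 3 × 3 = 9 interaction degrees of freedom, against 3 for a linear term, plus 2 more for the main effect. That is why linear should be the default. Results will also appear as curves, which are less compact than a subgroup table.

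### Q3 produces stratum-specific treatment effects only after a significant interaction in the same data, which exaggerates the reported differences on average unless true interactions are large

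*Protocol*

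**What the plan says.** All the relevant text is in the Protocol.

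- **Statistical methods for primary and secondary outcomes, Q3 paragraph.** The models will contain "interaction terms between patient subgroups (e.g., defined" "by baseline severity, structural metrics) and treatment types will be incorporated into" regression models. No condition is attached to fitting these terms, and the modifiers are given only as examples.
- **Same paragraph, next sentence.** The follow-on step is conditional: "Should significant interactions be detected", "stratified analyses will be performed".
- **Same section, opening.** Testing is done "with a two-sided significance level of" 0.05. No separate level is given for interactions.
- **Same section, Q2 paragraph.** Intervals are promised for "subsequent acute rupture, with results reported as hazard ratios or odds ratios and 95" per cent confidence intervals. The Q3 paragraph has no matching statement on what will be reported.
- **Sample size.** On the basis of patient volume, "a minimum of 500 participants is expected to be recruited", and this is "anticipated to provide sufficient statistical power for the planned multivariable analyses". No interaction effect, SD or power figure is given.

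**The concern.** The conditional sentence is a stated analysis rule, so it can be judged without the SAP. It lets one test decide which stratum effects are estimated, then estimates them from the data that produced the test result. An estimate kept because it crossed a threshold is, on average, further from zero than the truth. The difference between strata inherits this: the better-responding stratum looks better than it is, and the other looks worse.

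For Q3 the size of that difference is the result that matters. The question is which patients do better on which treatment, and the Research Project Statement says the registry should inform precision rehabilitation. Modifiers that fall short of significance have no planned level-specific effect, so a reader could not tell a small interaction from an imprecisely estimated one.

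**Working it through.** **The Protocol's own figure.** The 500 cannot be reproduced. It comes from patient volume, and no effect size, SD, power, number of treatments or subgroup share is given. Interaction power cannot be derived from the document.

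**Assumptions (not in the Protocol).** Two treatments, one binary modifier, a continuous outcome in SD units, no confounding, two-sided 0.05 (c = 1.96). N = 500 is taken as the number analysed. Let p_t be the share on one treatment and p_s the share in one subgroup.

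**Standard error of the interaction.** SE = sqrt(1 / [N p_t(1−p_t) p_s(1−p_s)]). With N = 500 and p_t = p_s = 0.5:

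- SE = sqrt(1/31.25) = 0.179 SD
- smallest significant estimate = 1.96 × 0.179 = 0.351 SD
- interaction detectable with 80% power = (1.960 + 0.842) × 0.179 = 0.501 SD

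**Mean estimate given significance.** With true interaction d and m = d/SE:

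- power = Φ(m−c) + Φ(−c−m)
- mean absolute estimate = SE × [mΦ(m−c) + φ(m−c) − mΦ(−c−m) + φ(c+m)] / power

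Example, d = 0.4: m = 2.236 and m−c = 0.276, so Φ = 0.609, φ = 0.384 and the opposite tail is negligible. The mean is 0.179 × (2.236 + 0.384/0.609) = 0.513 SD, and 0.513/0.4 = 1.28.

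| True interaction (SD) | Power | Mean absolute estimate if significant (SD) | Ratio to truth |
|---|---|---|---|
| 0.2 | 20% | 0.45 | 2.25 |
| 0.3 | 39% | 0.48 | 1.59 |
| 0.4 | 61% | 0.51 | 1.28 |
| 0.5 | 80% | 0.56 | 1.13 |
| 0.6 | 92% | 0.63 | 1.05 |
| 0.8 | 99% | 0.80 | 1.00 |

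**Sensitivity.**

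- 30/70 splits on both factors, N = 500: SE = 0.213. Ratios are 2.64 at 0.2 SD, 1.84 at 0.3, 1.24 at 0.5 and 1.02 at 0.8.
- 250 analysed, balanced: SE = 0.253. Ratios are 2.14 at 0.3 SD, 1.40 at 0.5 and 1.07 at 0.8.

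**On the VISA-A scale, assuming SD 20.** SE = 4 × 20/sqrt(500) = 3.58 points. A true 5-point differential (0.25 SD) is significant 29% of the time and then averages 9.2 points, 1.85 times the truth. A true 10-point differential (0.5 SD) is inflated 1.13 times.

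**Do the stratum effects themselves shift?** This was simulated with 400,000 replicates, 125 per treatment-by-subgroup cell and a stratum SE of sqrt(2/125) = 0.126.

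- True effects 0.40 and 0.20 average 0.52 and 0.08 once the interaction is significant.
- True effects 0.55 and 0.05 average 0.58 and 0.02.
- True effects 0.70 and −0.10 are essentially unchanged.
- With no true interaction, the 5% of data sets that pass show a mean absolute difference of 0.42 SD.
- Without the filter, the mean difference equals the true one in every case.

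**Why a fixed list matters.** If k independent interactions are all null, the chance that at least one passes at 0.05 is 1 − 0.95^k: 22.6% for 5, 40.1% for 10 and 64.2% for 20. The Protocol does not fix k.

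**The case against.** Testing the interaction before looking inside strata is a conventional safeguard against spurious subgroup claims, so the test is not itself an error. That stands, and the fix keeps the test. However, the safeguard limits which strata are examined; it does not make the effects it releases unbiased.

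A reader might infer that modifiers missing the threshold would have no estimate or interval at all. The text does not say so. The interaction terms are fitted unconditionally, only the stratified step depends on significance, and a SAP that is not shown may require full tabulation. What the Protocol does show is narrower: it plans no level-specific estimate for those modifiers, and its Q3 paragraph promises no interval.

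A reader might also infer that the published differences will be systematically exaggerated. That cannot be established from the document. The size depends on interaction power, which it does not give, and the bias nearly vanishes for large interactions.

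A third tempting step is to bar separate stratified models. This is a cohort with no randomisation described, and such models let confounder effects differ between strata, where a model with only a subgroup-by-treatment term holds them common. The gain in flexibility is paid for in precision, so barring them is not clearly an improvement.

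Finally, anyone who singles out significant interactions meets the same inflation, whether or not strata are refitted. That is true, but it is no reason to build the filter into the plan.

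**Conclusion.** The point holds as a conditional weakness in a stated rule. Used as written, the rule releases Q3 stratum effects through a significance filter on the same data, and their difference is overstated on average unless true interactions are large. At N = 500 in the balanced two-by-two case, the inflation is material (about 1.3 to 2.25 times) for true interactions of 0.2 to 0.4 SD, modest (1.13) at 0.5 SD, and 5% or less from about 0.6 SD. Uneven groups or fewer analysable participants make it larger. These factors rest on assumed effect sizes, group shares and numbers analysed. No figure in the Protocol is shown to be wrong, and no passages contradict each other. The change is worth making because complete reporting removes the selection bias at almost no cost.

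**What to change.** List the candidate modifiers in advance in place of the examples, and replace the conditional sentence in the Q3 paragraph with:

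> For every listed modifier, the interaction estimate and the treatment effect at each modifier level are reported with 95% CI from the interaction model, whatever the p-value; any separate stratified models are supplementary and labelled exploratory.

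The cost is a change of wording, agreement on the list and a longer results table. No new data are needed.
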